6.9 Sample Size Determination - Microbiome Sub-Study

Hypotheses will be tested at a global 5% Type 1 error rate (alpha) for each family of hypotheses, and we have chosen a completed sample (N=60) that will achieve at least 80% power using 2-sided tests. Our analysis of power is based on “effect size” (standard difference). We will control error in a family-wise manner, adjusting alpha using the Hochberg step up method for the number of tests within each hypothesis family. For **Aim 1**, we examined power using a preliminary longitudinal MANOVA to test for overall significance, and then examined the individual terms by bacteria or metabolite. If we have 12 to 18 taxa in our panel, we have 80% power for the overall test if two taxa make a 0.35-SD shift in abundance in response to smoking cessation. This assumes no within-subject correlation. Imposing a within subject correlation and using the jackknife variance estimate (clustered by subject) increases power. For follow-up testing, we will detect individual effects provided that at least one effect size exceeds ~ 1.3 .

Aim 2 examines whether the changes in the gut microbiome are associated with food intake and smoking abstinence at week 12. As with Aim 1, we will begin with the omnibus test using the multivariate pairwise distance measure (within subject) as a predictor. For the smoking outcome, we have 80% power to detect an odds ratio of 2.0, reflecting approximately a 20% difference resulting from a 1-SD change in pre-post distance. We also have 80% power to detect a correlation of 0.38, reflecting a 400 Kcal change in food intake. **Aim 3** begins with the model in Aim 2, above and explores interacting effects of treatment (BAS+ vs SC) on the relationship between gut microbiome changes, food intake and smoking abstinence. We will test an interaction effect predicting that the effects of gut microbiome changes (pre-post distance) on food intake and smoking abstinence will favor BAS+ versus SC. We have 80% power to detect a difference of 0.68 in the correlation of pre-post distance with food intake (0.68 versus 0), and a ratio of odds ratios (ORR) of 3.15, corresponding to a 25 to 30% greater change in abstinence for the BAS+ subjects.

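### The microbiome sub-study's 80% power figures for week-12 abstinence do not reproduce at N=60: a large shortfall for Aim 3, a near miss at best for Aim 2

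*Combined protocol and SAP*

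**What the plan says.** Section 6.9 sets the frame for all microbiome power statements: "we have chosen a completed sample (N=60) that will achieve at least 80% power using 2-sided tests". On error control it says "Hypotheses will be tested at a global 5% Type 1 error rate (alpha) for each family of hypotheses", with the adjustment described as "adjusting alpha using the Hochberg step up method for the number of tests within each hypothesis family".

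Aim 2 asks whether microbiome change is "associated with food intake and smoking abstinence at week 12". For abstinence the claim is "we have 80% power to detect an odds ratio of 2.0", expressed per SD of pre-post distance and equated with a difference of about 20%. For Aim 3, the treatment interaction, the 80% claim covers "a ratio of odds ratios (ORR) of 3.15, corresponding to a 25 to 30% greater change in abstinence for the BAS+ subjects".

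Section 6.12 specifies a logistic model for abstinence with pre-post distance as the omnibus predictor, and adds a treatment interaction for Aim 3. Section 3.3 plans equal numbers from the two arms. Neither section 6.9 nor section 6.12 gives an abstinence rate at week 12. The only assumed rates are the parent trial's 6-month figures in section 6.7: 13% with standard counseling and 25% with BAS+.

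**The concern.** Power in a logistic model depends on the outcome rate, so an 80% claim without a rate cannot be checked directly. It can be bounded, however. The information about a log odds ratio is proportional to p(1-p), which is largest at p = 0.5. If the claim fails at 50% abstinence, it fails at every rate, and the missing rate cannot explain the figure.

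What is at stake is how the abstinence results of Aims 2 and 3 are interpreted. A team that believes it had 80% power for these effects will judge the precision of its estimates differently from one that knows the figure was nearer 40-65%.

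**Working it through.** **Inputs.** From section 6.9: 60 completers, two-sided 5%, one binary outcome per person at week 12, OR 2.0 per SD (ln 2.0 = 0.6931) and ratio of ORs 3.15 (ln 3.15 = 1.1474). From section 3.3: equal arms, so 30 each. From section 6.12: logistic model, continuous predictor. The abstinence rate p is my assumption: 50% as the best case, then 25%, then 19%, the average of section 6.7's 13% and 25%. The week-12 rate may be higher than the 6-month rates.

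**Aim 2, large-sample formula.** SE = 1/√(60·p(1−p)); power = Φ(0.6931/SE − 1.96).

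**Aim 3, large-sample formula.** SE = √(2/(30·p(1−p))), with the same p in both arms; power = Φ(1.1474/SE − 1.96).

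| p | Aim 2 SE | z | Power | Aim 3 SE | z | Power |
|---|---|---|---|---|---|---|
| 50% | 0.258 | 2.685 | 76.6% | 0.516 | 2.222 | 60.3% |
| 25% | 0.298 | 2.325 | 64.2% | 0.596 | 1.924 | 48.6% |
| 19% | 0.329 | 2.106 | 55.8% | 0.658 | 1.743 | 41.4% |

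The stated 80% is not reached in any row, and the first row is the ceiling over all rates. With 25% and 13% abstinence by arm, Aim 3 power is 38.6%.

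**Sample size for 80% in the best case.** (1.96 + 0.8416)² = 7.849. Aim 2: 7.849/(0.25 × 0.6931²) = 65.3, so 66 completers. Aim 3: 2 × 7.849/(0.25 × 1.1474²) = 47.7 per arm, so 48 per arm or 96 in all.

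**Simulation.** The formula is optimistic at this size. With 20,000 simulated trials, a normal predictor and 50% abstinence, OR 2.0 gave 67.6% (Wald) and 71.3% (likelihood ratio); smaller runs reached about 73%. At about 22% abstinence the same OR gave 52% and 57%. For the ratio of 3.15 at 50%, power was 43.5-52.3% (Wald) and 50.3-56.8% (likelihood ratio). The lower end applies when the whole association sits in one arm, the upper end when it is split equally and in opposite directions.

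**Is the frame being read correctly?** Section 6.9's food-intake figures are a useful control. With Fisher's z at two-sided 5%, a correlation of 0.38 with 60 people gives 0.400 × √57 = 3.02, or 85.6% power. A difference of 0.68 versus 0 with 30 per arm gives 0.829/√(2/27) = 3.05, or 86.1%. Both meet the 80% claim under the same N, sidedness and alpha, so the problem is confined to the abstinence figures.

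**Do the percentage equivalents reveal the rate?** No. An OR of 2.0 moves a proportion by at most (√2 − 1)/(√2 + 1) = 17.2 points, against a stated figure of about 20. A ratio of 3.15 moves it by at most 27.9 points, within the stated 25 to 30. Neither helps, since even the best rate falls short.

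**The case against.** Several readings could rescue the figures.

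*More people.* Section 4.4 plans about 75 enrolled, and section 4.2 counts those lost to follow-up as smokers, so some non-completers might enter the abstinence model. With 75 people, two-sided 5% and 50% abstinence, the formula gives 85% for OR 2.0 but only 70% for 3.15. Section 6.9 bases its claim on 60 completers, so this softens the practical consequence for Aim 2 without making the statement correct.

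*One-sided testing.* With N=60 at 50% abstinence this gives 85% and 72%. It contradicts the stated two-sided tests and still misses for Aim 3. The 3.15 figure appears only with 75 people, a one-sided test and 50% abstinence together (79.9%).

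*Repeated measures.* Section 6.12 names generalized estimating equations, and section 6.5.6 lists abstinence at weeks 8 and 12. Two time points with within-person correlation ρ multiply the effective N by 2/(1+ρ). Aim 2 needs 66/60 = 1.10, so ρ of about 0.82 or less, which is quite possible. Aim 3 needs 96/60 = 1.60, so ρ of about 0.25 or less. Section 6.9 names week 12 only and describes no pooled calculation.

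What stands is that Aim 2 at 50% abstinence is close by formula: the detectable OR is 2.06 against the stated 2.0. It should not be given the same weight as Aim 3.

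Two stronger inferences are not supported. A reader might suppose that the calculations were planned at alpha 0.025, which would lower the ceilings further. Section 6.9 states a global 5% with a step-up procedure, whose first step tests the largest p-value at 5%, and section 6.12 retains Aim 3 interactions at p<0.05. A reader might also suppose that a null result will be taken as evidence against H2 and H3. The documents say nothing on how a null would be read.

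**Conclusion.** The concern holds for both figures, but unequally. For Aim 3, 80% power for a ratio of odds ratios of 3.15 is wrong by a wide margin at every abstinence rate: at most 60% by formula and about 43-57% by simulation at 50% abstinence, and 49% and 41% by formula at 25% and 19%. For Aim 2, 80% power for an odds ratio of 2.0 is a near miss by formula at 50% abstinence (77%, or about 68-73% simulated) and a substantial shortfall at 25% (64%) and 19% (56%).

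This rests on one week-12 outcome per person, 60 completers in equal arms, a roughly normal standardized predictor, no covariates and two-sided 5% tests. The lower abstinence rates are illustrative, because the plan gives none for week 12.

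The reach is limited. Section 2.3 labels Aim 3 exploratory, the sub-study is an add-on, and nothing here touches the parent trial's sample size or primary outcomes. It would be wrong to infer that the sub-study's power statements fail as a whole, since the food-intake figures hold.

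**What to change.** In section 6.9, state the assumed week-12 abstinence rate, by arm for Aim 3, and the calculation method. If repeated outcomes or non-completers are meant to contribute, say so and give the assumed correlation or N. Then restate either the power for the present effects or the effects detectable at 80%, checked by simulating the planned logistic model.

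The formula values should not simply be substituted. An OR of 2.06 at 50% abstinence, 2.3 at 25%, and a ratio of 4.3 at 50% gave only about 71-75%, 70-75% and 59-76% power when simulated. As a guide from simulation at 80% power with 60 completers:

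- Aim 2: OR about 2.2 at 50% abstinence and about 2.5-2.6 at 25%.
- Aim 3: ratio of ORs about 5 to more than 6.5 at 50%, depending on the test and on how the effect splits between arms, and larger at lower rates.

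The cost is less favourable stated figures. No extra participants, visits or samples are needed.

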6.10 Statistical Methods - Parent (Main) Study

Prior to the analyses, we will: (a) screen the data for data-entry errors, (b) check for outliers, and (c) assess the extent and type of missing data, and select the most appropriate method for dealing with the missing data (e.g., multiple imputation, all available data). We will create all summary scores needed for analysis, and check that distributional assumptions are met. We will assess for participation biases, attrition differences and treatment adherence (controlled for in primary analyses) across treatment arms. Main effects and moderated effects analyses will be conducted using Stata software (StataCorp, College Station, Texas) and mediation analyses will be evaluated using Mplus software 7.2.

Aim 1 will evaluate smoking abstinence (point-prevalence, binary outcome) and PCWG (kg weight gain, continuous outcome) in the context of a longitudinal model with categorical and continuous predictor variables. We will use generalized linear models fitted with random effects using Generalized Estimating Equations. We will specify the logistic model for the binary abstinence outcome, and Gaussian weight gain outcome. Models will include treatment assignment, time point, adherence measures, and covariates related to the outcome in

CONFIDENTIAL

This material is the property of the University of Pennsylvania. Do not disclose or use except as authorized in writing by the study sponsor

preliminary analyses. Comparisons are all between-subjects. We will test for interaction between treatment and time point using the Wald Chi-square, and estimate a common odds-ratio across time points if they show no evidence of differing across time. The primary hypothesis will be tested using the z-score corresponding to treatment assignment at EOT, and at 12- and 26-weeks post quit, with the primary test of hypothesis 1a at 26-weeks post-TQD. Consistent with ITT analyses, we will measure smoking cessation and weight gain in the full sample at the 26-week follow-up, evaluating a smoking status (days x rate) by treatment interaction for the PCWG analysis (H.1.b.). The **exploratory aim** will evaluate variables that modify the effect of treatment on smoking cessation and PCWG. We will enter interaction terms (e.g., treatment x depression) to the models generated for Aim 1. The interactions will be retained if the z-score is significant ($p<0.05$). We will focus first on EOT, then the 12-week and 26-week follow-up time points, and finally the combined effect across time point.

Aim 2 will involve assessing the direct effect of treatment on smoking cessation and PCWG, and the indirect or mediated effects of treatment on these outcomes through the hypothesized sequential mediating mechanisms using structural equation modeling. Mediation exists when a relationship between treatment and smoking cessation or PCWG is accounted for in full, or in part, by one or a set of intervening variables (e.g., alternative reinforcers, food cue-induced craving, food reward, RRVF). Longitudinal change in the mediators will be represented with a slope factor (based on observed repeated measures of each mediator). We will assess the mediation strength (absent to complete) by estimating the effect proportion mediated ($\beta_{\text{indirect}}/\beta_{\text{total}}$), and determine the significance of effects with Delta method standard errors, with bootstrapped standard errors for validation. We will employ a weighted least squares estimation technique with robust standard errors, and a mean and variance adjusted chi-square test for the estimation of model parameters. Multiple indicators of model performance will be used, including the χ^2 test, Comparative Fit Index ($< .95$), Weighted ($<.90$) and Standardized Root Mean Square Residual ($<.80$), Root Mean Squared Error of Approximation ($< .05$), and an examination of standardized model residuals. Bayesian Information Criterion and Scaled Unit Information Prior BIC will be used to compare different models.

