Behavioral Activation Intervention (BAS+): SC is incorporated into BAS+ in an additive design to cover best practice guidelines for smoking cessation. The goal of the BAS+ is to maintain a level of overall reward after cessation by structuring and enhancing opportunities for reinforcement to: (1) ensure that not smoking is as reinforcing as smoking; and (2) prevent an over-reliance on food as a substitute reinforcer for smoking so that PCWG does not precipitate smoking relapse. The unique treatment components of BAS+ include facilitating the identification and engagement in a variety of rewarding activities (other than eating and not associated with smoking) and maximizing the enjoyment derived from these rewarding activities. As such, this intervention should benefit all smokers trying to quit, not just those participants who feel that preventing PCWG is meaningful.

In the initial session (week -2, Baseline), the counselor will discuss why smokers easily substitute snacking for cigarettes after smoking cessation, and the consequences for weight gain and continued abstinence. The treatment rationale for promoting smoking cessation and preventing PCWG will focus on structuring a variety of reinforcing activities to promote a more rewarding nonsmoking lifestyle; one that has many rewarding options besides food. By replacing the pleasure previously derived from smoking, the participant will miss cigarettes less, rely less on calorie-dense snacks, gain less weight, and be less likely to return to smoking. The counselor will introduce daily activity monitoring and the identification of values and goals in several life domains (e.g., family and intimate relationships, employment/career, hobbies, recreation, spirituality). The daily activity monitor promotes awareness of time spent in important and or enjoyable activities and their association with smoking. The identification of values and life goals will be used to identify rewarding activities consistent with helping one live according to his or her values. Participants will be assisted in identifying rewarding activities (i.e., alternative reinforcers, not linked to smoking) in important life domains through a life activities checklist.

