Positive and Negative Affect (PANAS): The Positive and Negative Affect Schedule (1-week frame of reference), a 20-item Likert-format self-report questionnaire, will be used to measure positive mood and negative mood. The two subscales have 10 items each, are internally consistent in both nonpsychiatric and psychiatric samples ($\alpha = .79$ to $.91$), and exhibit good convergent and discriminant validity.

Withdrawal Symptoms (MNWS): The Minnesota Nicotine Withdrawal Scale - Revised version (MNWS-R) will measure withdrawal symptoms ($n=15$) associated with quitting smoking. Participants will rate the intensity of their symptoms on the following scale: 0 = none, 1 = slight, 2 = mild, 3 = moderate, 4 = severe and a summary score will be calculated. The MNWS with a 1-week frame of reference will be utilized throughout the trial.

Smoking Urges/Craving (QSU-B): The well-validated and reliable 10-item brief Questionnaire of Smoking Urges will assess craving for cigarettes. The QSU-B utilizes a "right now" frame of reference.

Hedonic Capacity (SHAPS): Hedonic capacity will be measured with the 14-item Snaith-Hamilton Pleasure Scale (SHAPS). Participants will rate the degree of enjoyment they would get from hypothetical activities typically experienced as enjoyable. The SHAPS loads strongly on

CONFIDENTIAL

This material is the property of the University of Pennsylvania. Do not disclose or use except as authorized in writing by the study sponsor

measures of anhedonia ($r = .92$), is internally consistent ($\alpha = .87$), stable over time, and has adequate convergent and discriminant validity in clinical and nonclinical populations.

Treatment Adherence: Treatment adherence is defined as attending 6 of 8 counseling sessions and using 6 or more patches on average per week. TN adherence will be assessed and recorded at every in-person visit over the treatment period.

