6.7 Sample Size Determination- Parent (Main) Study

For **Aim 1** we hypothesize that BAS+ vs. SC will have higher smoking abstinence rates and less PCWG at the 26-week follow-up (primary outcomes). Power calculations were all approximated as t-tests or z-tests, and conducted using PASS Software (Power and Sample Size, NCSS Software, Kaysville, UT), Bonferroni corrected for two primary outcomes ($p=.025$). Proportions of abstinent and smoking subjects will be compared using the log of the odds-ratio, which has a known variance. Informed by smoking cessation counseling plus TN research, we anticipate that the 6-month abstinence rate will be 13% in the SC (control) group and 25% in the BAS+ group (consistent with a persistent effect of BAS+ after the discontinuation of TN). A sample of 213 per group provides 82% power to detect this 12% difference in quit rates at 6 months. This represents a clinically meaningful effect and corresponds to a small effect size ($\delta=.15$). For PCWG, we will include all participants in the analysis, while testing a smoking status x treatment interaction. Informed by epidemiological and clinical studies of PCWG, we will have 80% power to detect a 6 pound (2.72 kg) difference in PCWG between BAS+ and SC, using the interaction term. We expect BAS+ vs. SC will have less post-cessation food intake (secondary outcome) at the 26-week follow-up. We have 80% power to detect a 320 kcal/day difference between the two groups ($p = .05$). In light of these considerations (i.e., 213 subjects per arm; total 426) and an attrition estimate of 15% across accrual, we will recruit a total of 245 subjects to each arm for a total of 490 subjects (~500).

For **Aim 2**, we hypothesize that BAS+ vs. SC, will increase alternative reinforcers, and reduce food reward, the RRVF, and food cue-induced craving. These changes, in turn, will predict less food intake and PCWG, and greater smoking abstinence at the 26-week follow-up. Using structural equation modeling, we will test the treatment effect on the slope of the mediators versus time, with pre-quit values representing the intercepts. We will examine the proportion of

CONFIDENTIAL

This material is the property of the University of Pennsylvania. Do not disclose or use except as authorized in writing by the study sponsor

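### Both primary models adjust for adherence measured after randomisation, so the treatment coefficient tested is not the intention-to-treat effect

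*Combined protocol and SAP*

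**What the plan says.** Section 6.10 (Statistical Methods, Parent Study) brings adherence into the primary analyses twice. Among the preliminary data checks it lists "treatment adherence (controlled for in primary analyses) across treatment arms". Then, directly after specifying a logistic model for abstinence and a Gaussian model for weight gain, it says "Models will include treatment assignment, time point, adherence measures, and covariates related to the outcome in" preliminary analyses. The second statement therefore covers both primary outcomes.

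Section 6.5.2 gives the definition: "Treatment adherence is defined as attending 6 of 8 counseling sessions and using 6 or more patches on average per week".

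On the test, Section 6.10 says "The primary hypothesis will be tested using the z-score corresponding to treatment assignment at EOT, and at 12- and 26-weeks post quit", with week 26 as the main time point. It goes on: "Consistent with ITT analyses, we will measure smoking cessation and weight gain in the full sample at the 26-week follow-up". Section 3.1 uses the same ITT language.

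The sample size in Section 6.7 rests on a different quantity: "Proportions of abstinent and smoking subjects will be compared using the log of the odds-ratio, which has a known variance". On that basis, "A sample of 213 per group provides 82% power to detect this 12% difference in quit rates at 6 months".

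**The concern.** Randomisation follows the Intake Visit (Sections 3.1 and 9.3). The first session of the assigned counselling is at the Baseline Visit (Section 6.2.3), and patches run from week 0 to week 8 (Section 5.2). Every component of adherence therefore comes after assignment and can respond to it. The session schedule and patch regimen are the same in both arms, but the sessions are not: "SC is incorporated into BAS+ in an additive design to cover best practice guidelines for smoking cessation". Attending six sessions means receiving a different treatment in each arm, and BAS+ could raise or lower attendance.

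Two things go wrong if adherence differs by arm.

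- Any benefit that BAS+ delivers through better attendance or patch use is removed from the coefficient. If BAS+ lowers adherence, the coefficient is inflated instead.
- If adherence and quitting share causes such as motivation, the model compares people who are no longer balanced by randomisation. The coefficient can then be non-zero when the randomised effect is zero.

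This trial also builds in a link between adherence and outcome. Participants lost to follow-up count as smokers (Section 4.2), and early dropouts also miss sessions. Patch adherence is recorded at in-person visits (Section 6.5.2), so it may be missing for people whom the ITT statement includes.

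A lesser, separate point is that the other covariates are chosen by their relation to the outcome. They are not limited to pre-listed baseline variables, and nothing guarantees that the stratification factors of Section 3.1 (nicotine dependence, BMI, gender) enter the model. That bears on precision and standard errors, not on ITT status.

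**Working it through.** **Inputs from the documents (Section 6.7):** 213 per arm; 13% abstinent on SC and 25% on BAS+; alpha 0.025. Sidedness is not stated for the parent study. Two-sided, with critical value 2.241, reproduces the plan's figure.

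**The plan's own figure.** For a two-proportion z-test the pooled rate is 0.19.

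- Null SE = √(2 × 0.19 × 0.81 / 213) = 0.0380
- Alternative SE = √((0.13 × 0.87 + 0.25 × 0.75) / 213) = 0.0376
- Power = Φ((0.12 − 2.241 × 0.0380) / 0.0376) = Φ(0.926) = 82.3%

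The stated 82% is reproduced. On the log-odds scale:

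- OR = (0.25/0.75) / (0.13/0.87) = 2.23, log OR = 0.802
- SE = √(1/(213 × 0.13 × 0.87) + 1/(213 × 0.25 × 0.75)) = 0.258
- Power = Φ(0.802/0.258 − 2.241) = 80.8%

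Both are unadjusted comparisons by assigned arm.

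**Adding a binary adherence term (assumed inputs).** The documents give neither adherence rates nor the adherence-abstinence association. I hold the arm totals at 13% and 25%, let p be the adherent proportion in an arm and θ the adherence-abstinence odds ratio, and solve for the non-adherent rate q₀ and adherent rate q₁:

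- p·q₁ + (1 − p)·q₀ = arm total
- q₁/(1 − q₁) = θ·q₀/(1 − q₀)

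The adjusted treatment OR is the ratio of the non-adherent odds in the two arms. Its SE comes from the logistic information matrix at 213 per arm.

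Worked case: SC adherence 55%, BAS+ 65%, θ = 4.

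- SC: q₀ = 0.0557, q₁ = 0.1908 (check: 0.45 × 0.0557 + 0.55 × 0.1908 = 0.130)
- BAS+: q₀ = 0.1081, q₁ = 0.3264 (check: 0.35 × 0.1081 + 0.65 × 0.3264 = 0.250)
- Adjusted OR = (0.1081/0.8919) / (0.0557/0.9443) = 2.06, SE 0.264
- Power = Φ(0.720/0.264 − 2.241) = 69%

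Other cases, SC adherence 55% throughout (adjusted OR, power):

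| BAS+ adherence | θ = 2 | θ = 4 | θ = 8 |
|---|---|---|---|
| 45% | 2.42, 87% | 2.69, 92% | 3.01, 96% |
| 55% | 2.26, 81% | 2.34, 83% | 2.44, 85% |
| 65% | 2.11, 74% | 2.06, 69% | 2.03, 65% |
| 75% | 1.98, 64% | 1.83, 51% | 1.73, 42% |

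A simulation with 20,000 replicates per scenario agrees to within about two points of power for θ of 4 and 8. The rise above 2.23 at equal adherence is non-collapsibility of the odds ratio, not confounding.

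**No true effect.** In the same kind of simulation, abstinence is 13% in both arms and SC adherence is 55%. A latent motivation adds 1 to 1.5 per SD to the log-odds of both adherence and abstinence. Rejection against the nominal 2.5% is:

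| Adherence gap | Rejection | Spurious OR |
|---|---|---|
| 0 points | 2.3–2.5% | none |
| 5 points | 2.4–2.8% | not tabulated |
| 10 points | 2.7–3.5% | 0.89–0.93 or 1.08–1.13 |
| 20 points | 4–8.5% | 0.80–0.87 or 1.17–1.31 |

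**Weight.** Ignoring the smoking-status term, the linear identity is: shift = −(adherent minus non-adherent weight gain) × (adherence gap). An assumed 2 lb × 0.10 gives 0.2 lb, and 4 lb × 0.20 gives 0.8 lb, in either direction. The target difference is 6 lb.

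**The case against.** The plan attaches ITT to measuring outcomes in the full sample and counts losses as smokers. It makes no explicit claim about an ITT estimand, and Section 6.7 describes an unadjusted comparison. That is a fair reading of the ITT phrase, but it settles who is analysed, not what the coefficient means. Section 6.7 explains the sample size; the analysis model is the one in Section 6.10.

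No passage predicts an adherence gap, and the number of sessions, the patch regimen and the visit payments are the same in both arms. Extra content in BAS+ shows that a gap is possible, not that there will be one. With equal adherence the null is preserved and power is not lost. This stands, but the plan does not assume equal adherence and intends to examine it by arm.

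The illustration depends on the assumed odds ratio and uses one binary term at one time point, whereas the plan has several adherence measures in a longitudinal model. This also stands. At an odds ratio of 2 the loss is smaller, though a 10-point gap still leaves 74% power.

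For weight, the planned smoking status by treatment term is itself post-randomisation, so removing adherence alone does not give a plain ITT coefficient there. That is correct, and it makes the case strongest for abstinence.

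**Conclusion.** The concern holds and should be fixed before analysis. The text is unambiguous: adherence is in both primary models, it is measured after randomisation, the treatment coefficient from those models decides the primary hypotheses, and no analysis without adherence is specified. That conclusion needs no assumption. The 82% power figure is correct, but for the unadjusted contrast and not for the test Section 6.10 describes.

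The size does rest on assumed adherence rates and associations. For abstinence, a 10-point gap in favour of BAS+ takes power from about 81% to 65–74%, and a 20-point gap to 42–64%. A 10-point gap the other way inflates the odds ratio to 2.42–3.01. False-positive inflation is slight at 10 points and material only near 20. The illustrated weight shift is small. Because no adherence rates are given, the direction cannot be known in advance.

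**What to change.** In Section 6.10, delete the parenthetical remark that adherence is controlled for in primary analyses, and replace the sentence listing model terms with:

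> Primary models include treatment, time point, treatment by time point, the randomisation stratification factors (nicotine dependence, BMI, gender) and, for weight, pre-cessation weight. Apart from the smoking status by treatment term specified below for weight, any further covariates are pre-listed baseline variables. Adherence is not included.

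Report adherence by arm, and use it only in a labelled secondary analysis such as a complier-average effect. The rules that follow in Section 6.10, including the common odds ratio when treatment effects do not differ over time, can stay. Whether to keep the smoking-status term for weight is a separate question that this wording leaves open.

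The cost is SAP wording only, with no new data. The 82% statement already refers to the unadjusted assigned-arm contrast. Adjusting for baseline factors changes the odds ratio scale slightly but keeps the comparison by randomised arm. The weight power statement still refers to its interaction term. The one loss is that the adherence-adjusted result becomes secondary.
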